### Randomization

Using the randomization approach described below, there will be random or minimally biased assignment of subjects to study arms. Randomization will be achieved through a blocked design utilizing permuted blocks of random sizes. The design ensures equal representation of treatment assignment across groups and protects the study team and investigators from easily anticipating treatment allocation. Randomization to CHAMPS Pilot or standard of care is 1:1. Participants will be randomized using computer-generated random numbers at baseline. The randomization database will be stored on a password protected computer at Columbia University and will only be accessible to PI [name]. Following completion of the informed consent and baseline assessment, participants will be randomly assigned to one of two trial arms in REDCap.

### Procedures

All study visits will occur remotely via Zoom. Staff members will collect digital informed consent prior to enrolling into the study trial (See Protection of Human Subjects). The informed consent form provides details of the study procedures, risks, benefits, site contact information, and the nature of confidentiality and voluntary participation. The consent process also covers information on the study and compensation for time.

Participants in both the intervention and control arms will complete remote visits at the baseline and 3-month follow-up. Following the completion of the baseline study instruments, study participants in the CHAMPS Pilot intervention arm will be mailed a CleverCap™ Lite dispenser and trained on how to use it; they will also be trained by study team members on how to use the different features of the Wise App and receive medication reminders. Upon assignment to the intervention arm, a CHW is assigned to and meets with the participant as soon as possible, generally on the same day but no more than five business days. The CHW will deliver the interventions outline in Table 3 remotely throughout the course of the study. Participants will also be provided the opportunity to complete a follow-up interview at their follow-up visit. Follow-up interviews will be recorded via Zoom and will be semi-structured. Study staff members will take field notes and interview recordings will be transcribed prior to analysis.

Dried Blood Spot (DBS) kits will be used to measure participant viral load. DBS kits will be shipped to participants, allowing them to collect their sample in their home or other secure environment. Instructions will be included with the kit, including information about how to collect the dried blood spot and how to mail the sample back to the research team. Participants will be instructed to call research staff to confirm they have

received the kit, have collected the sample, and have mailed the sample back, as well as if they have any questions.

Participants will be texted appointment reminders for study visits. Hard to reach participants will also be sent scheduling reminders. These reminders will be sent via Qualtrics, REDCap and/or encrypted e-mails from the study's secure CUMC e-mail address.

Participants in both arms will receive \$40 at baseline and \$50 at 3-months as a token of appreciation for their time participating in the study visits and for their dried blood spot samples. Participants electing to complete follow-up qualitative interviews will receive an additional \$35.

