However, CHW models do not provide strong evidence for improving key psychosocial or HIV health outcomes associated with ART adherence and viral suppression, e.g., HIV-related stigma, quality of life, psychosocial distress/stress, adherence medication and skills, and adherence self-efficacy. Prior work suggests that it is the *enhanced relationship* between CHW and PLWH that is vitally important and is associated with improvements in linkage to care, retention in care, and viral suppression. In our BA2C RCT, CHW delivered an intervention adapted from ARTAS, a CDC evidence-based intervention (EBI) show to significantly increase both linkage to and retention in care. While ARTAS was developed for new-to-care PLWH, BA2C was tailored and adapted for PLWH who had previously linked to but were not currently engaged in care. BA2C results showed that participants in both the intervention and comparison groups improved across multiple outcomes (linkage to care, retention in care, ART prescription, and viral suppression), but there was no significant difference between groups. Some of the limitations of the BA2C study included poor retention rates (70%) and difficulty attending CHW intervention sessions, suggesting that a hybrid intervention in which CHW sessions can be delivered through a mobile platform has the potential to improve the efficacy of the intervention. Given the limitations of the BA2C intervention and in direct response to RFA-NR-20-002, *Strengthening the Impact of Community Health Workers on the HIV Care Continuum in the US*, we will leverage our mHealth work to overcome the limitations of the BA2C study. Namely, we will use mHealth technology to overcome logistic hurdles of connecting participants and their CHW and to improve engagement through the tools in our CleverCap App.

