The ubiquitous nature of mHealth technologies in daily life creates opportunities for health behavior management tools that were not previously possible and has the potential to address many of the healthcare needs of PLWH. The use of mHealth can reduce geographic and economic disparities and personalize healthcare, which is particularly relevant to PLWH since a majority represent underserved and minority groups. mHealth technology is especially important in the context of improving ART adherence in PLWH. There is preliminary evidence that mHealth technology is a feasible, attractive, accessible, and effective platform for improving ART adherence in PLWH. Eighty-one percent (81%) of Americans are smartphone

owners, and there is evidence that underserved populations use smartphones as their primary method for accessing the Internet. Finally, there is evidence that mHealth technology can promote the prevention and management of chronic illnesses such as HIV, thereby allaying weaknesses of the BA2C intervention.

The proposed study will pilot test a remotely delivered intervention, **Community Health Worker And MHealth to ImProve Viral Suppression (CHAMPS Pilot)**, in 40 PLWH in the US.

Aim 1. To assess the feasibility of the CHAMPS Remote Intervention.

Aim 2. Conduct follow-up interviews to assess the barriers and facilitators to the recruitment, enrollment and retention procedures and to understand the acceptability of the intervention.

[figure not shown]
This study seeks to expand and strengthen a CHW model through an extant mHealth approach. The pilot study also seeks to establish the feasibility of administering this intervention remotely. Findings will inform the effect of *CHAMPS Pilot* on outcomes related to the HIV Care Continuum in EHE priority settings.

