### Design Overview

A pilot study will be conducted with 40 PLWH over 3 months. Participants will be randomly assigned to CHAMPS Pilot (intervention) or a standard-of-care control arm.

**Intervention Arm:** The CHAMPS Pilot intervention, outlined in Table 1, is a 3-month intervention guided by BA2C. The CHW will be demographically-matched to our study participant.

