### Sound Retention Efforts

Using the retention efforts described above and in the Recruitment and Retention attachment, we are confident that we will retain at least 80% of our study sample at the follow-up assessments as we have done previously.

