## **Data Analysis**

The distribution of all variables will be assessed, as will the correlations between all variables and the primary/secondary outcomes. We will assess for patterns of missing data, which are expected to be low as the study utilizes computer-assisted self-interview (CASI) for sensitive data, which reduces participant nonresponse. The primary anticipated reason for missing data is attrition due to loss to follow-up. Based on our preliminary studies, we are accounting for 20% attrition from randomization to the 3-month assessment.

All multivariate analyses will be preceded by standard descriptive bivariate analyses to describe key variables and relationships among them. These analyses will include means, frequency tables, histograms, and examination of distributions. All statistical tests will be two-sided tests with the level of significance at 0.05. The primary hypothesis 1 will be a comparison of viral suppression (primary outcome) between CHAMPS Pilot and standard of care. We will also compare the drop in viral load (measured in logarithmic scale with base 10) between the two groups. Our secondary and related outcome is ART adherence measured in two ways: 1) a single-item self-report measure, an empirically validated instrument (SRSI) and 2) electronic pill bottle data which we will be collecting in the intervention group since all participants will receive a CleverCap bottle for their medications. All the analyses will be based on initial assignment to groups, using the intention-to-treat principle.

The primary hypothesis 1 ( $H_1$ ) will be tested using a generalized linear mixed model (GLMM) with logit-link function for binary outcomes (i.e., viral suppression) or a linear mixed model (LMM) for continuous outcomes (i.e., viral load measured in logarithmic scale) to account for the non-independence of repeated measurements within individuals. The models will include a random intercept and fixed effects for intervention group, time, and interaction term of group and time which is for testing efficacy of the intervention. The model may include

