### Human Subjects Involvement, Characteristics, and Design

#### Characteristics of the Population:

The trial will involve the recruitment and retention of men and women ( $n=40$ ) with HIV infection who are virally unsuppressed in the United States. Study volunteers must meet general criteria to be eligible for further screening for participation in the study. In most cases, this information will be acquired during a telephone interview prior to a screening/consent remote visit. *The inclusion and exclusion criteria have been carefully*

*selected to enroll the most appropriate study population while also ensuring the generalizability of the findings.* All participants will engage in a 3-month randomized adaptive intervention. The total study duration will be 3 months. A maximum of 25 follow-up interviews will be conducted, with an oversampling of participants in the intervention group.

Potential participants will be recruited online using social media platforms. Persons living with HIV (PLWH) will be included if they meet the following eligibility criteria:

There are limited inclusion criteria in order to support the generalizability of our findings.

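### The plan states no interview route for randomized participants who withdraw or miss the 3-month visit, although Aim 2 asks about barriers to retention

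*Combined protocol and SAP*

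**What the plan says.** Aim 2, in Study Purpose and Rationale and again before the qualitative analysis section, is: "Conduct follow-up interviews to assess the barriers and facilitators to the recruitment, enrollment and retention procedures and to understand the acceptability of the intervention".

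The Procedures section says when the interview is offered: "Participants will also be provided the opportunity to complete a follow-up interview at their follow-up visit". The same section sets the visit schedule: "Participants in both the intervention and control arms will complete remote visits at the baseline and 3-month follow-up". There is therefore one follow-up visit. Overview of Data Collection Time Points allows it to fall up to 30 days either side of target.

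Characteristics of the Population gives the interview number and the only sampling rule: "A maximum of 25 follow-up interviews will be conducted, with an oversampling of participants in the intervention group". The interview is elective and carries an extra $35 (Procedures).

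On loss to follow-up, the quantitative Data Analysis section names attrition as the main anticipated cause of missing data and states: "we are accounting for 20% attrition from randomization to the 3-month assessment".

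The supplied text describes no exit interview, withdrawal interview or interview after a missed visit, and no sampling by retention status.

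**The concern.** For the retention question, attendance at the 3-month visit decides who is offered an interview, and attendance is also what is being studied. Staff who follow the procedure as written will interview only people who were retained. Those people can describe obstacles they overcame. They cannot describe first-hand the obstacles that led someone else to leave.

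This matters more here than in most pilots. The rationale reports that the predecessor trial (BA2C) suffered from "poor retention rates (70%) and difficulty attending CHW intervention sessions", and the mobile component is added to overcome those problems. The qualitative section says the interview findings will inform changes to the intervention. If the participants the remote format failed to keep are not heard, the next trial could carry forward a retention problem that nobody examined.

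**Working it through.** The documents give no derivation of the interview number, so there is no figure of the plan's own to reproduce. The check is a head count of who can reach an interview under the written procedure.

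**Inputs**
- Sample size N = 40 (Design Overview: "A pilot study will be conducted with 40 PLWH over 3 months"), randomized 1:1 (Randomization), so about 20 per arm.
- Planned attrition d = 0.20 (Data Analysis). Sound Retention Efforts agrees: "we are confident that we will retain at least 80% of our study sample at the follow-up assessments".
- Sensitivity value d = 0.30, from the predecessor's 70% retention. That study is not a close match, so this is not a forecast.
- Interview cap C = 25, intervention arm oversampled (Characteristics of the Population).

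**Step 1. People with no stated route: N × d**
- Planned: 40 × 0.20 = 8, about 4 per arm if loss is equal.
- Sensitivity: 40 × 0.30 = 12, about 6 per arm.

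**Step 2. People who attend and can be offered an interview: N × (1 − d)**
- Planned: 40 − 8 = 32, about 16 per arm.
- Sensitivity: 40 − 12 = 28, about 14 per arm.

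**Step 3. Can attendees alone fill the cap?**
- Planned: 25 ≤ 32, if 25/32 = 78% of attendees accept.
- Sensitivity: 25 ≤ 28, if 25/28 = 89% accept.
- Oversampling the intervention arm does not prevent this. With equal loss, 16 intervention + 9 control = 25 at 20% attrition, and 14 + 11 = 25 at 30%.

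The cap can therefore be met with 0 of the 8 (or 12) non-retained people interviewed. If fewer attendees accept, slots stay empty, but nothing in the text directs them to non-attenders.

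**Step 4. A reference point.** If 25 interviewees were a simple random draw from all 40 randomized, the expected number not retained would be C × d:
- Planned: 25 × 0.20 = 5.
- Sensitivity: 25 × 0.30 = 7.5.

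The written procedure gives 0. Step 4 is illustrative only, because the plan oversamples one arm, participation is elective, and some lost participants could not be reached.

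**The case against.** The strongest reply is that the text sets no bar. It says an opportunity will be given at the visit and does not say that no other interview may take place. Sound Retention Efforts also points to a recruitment and retention attachment that is not among the supplied documents. A reader might infer that lost participants are excluded and that all of Aim 2 will rest on completers. The documents do not support that. They support the narrower statement that no route is given for these participants.

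Other parts of the reply also stand:
- **Attending is not the same as completing the intervention.** Someone who stopped community health worker sessions or app use can still be interviewed if they attend one Zoom visit in a wide window.
- **Most of Aim 2 is within reach of attendees.** They can speak to their own recruitment and enrollment, to what helped them stay, and to much of acceptability.
- **The direction of bias is not established.** A reader might infer that the findings will certainly look too favourable. Nothing in the documents ties loss to dissatisfaction. With equal loss, about half of those lost would be controls, who cannot comment on an intervention they did not receive.
- **The figure of 12 transfers poorly.** The predecessor had 10 to 12 visits over six months, an initial face-to-face meeting and outcomes to 12 months. This study is remote and lasts 3 months.
- **Some lost participants will be unreachable** for an interview too.

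The reply does not close the gap. The Recruitment Plan's tracking of reasons covers people who decline to join, not those lost after randomization. Reminders to hard-to-reach participants serve visit scheduling. Encounter notes, app and pill-bottle usage and medical record data (Study Procedures and Materials) can show that someone disengaged, but they do not replace that person's account of why. Some people who withdraw or miss the visit may still be contactable.

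**Conclusion.** The concern holds in a limited form. As written, the plan's interview evidence on retention would come only from people who attended the 3-month visit. About 8 of 40 participants would have no stated route to an interview at the planned 20% attrition, and 12 of 40 only as a sensitivity value. The 32 (or 28) attendees are enough to fill all 25 slots.

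The weakness lies mainly in the retention component of Aim 2. An effect on acceptability is possible but depends on whether dissatisfied participants are the ones who leave. The primary outcome, randomization and safety are not affected. The conclusion assumes that no interview route for non-attenders exists in material not supplied, such as the retention attachment. If one does, the Procedures section should say so. This is a cheap improvement to one of the study's two aims, and worth making.

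**What to change.** 1. In Procedures, offer the interview independently of visit attendance: by phone or Zoom, at the existing $35, to participants who withdraw or miss the 3-month visit.
2. In Characteristics of the Population, keep some of the 25 slots open for them, and release unfilled slots to attendees. About 5 would match the proportional share at 20% attrition. The number is an example and does not come from the plan.
3. In the report of Aim 2, state how many interviewees were not retained, so that readers can judge how far the retention findings reach. With about 5 such people, a formal comparison by retention status would be thin and need not be promised.

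The change stays within the existing interview cap and payment. Its cost is extra contact attempts, some of which will go unanswered, and possibly a few fewer attendee interviews. It is best settled before follow-up begins, since people who leave are likely to become harder to reach with time.

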### Overview of Data Collection Time Points

Follow-up visits will be scheduled 30 days before to 30 days after the target window based on participant availability and site capacity. Timing of follow-up visits is scheduled to allow site flexibility while still scheduling follow-up visits within a reasonable time span.

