**Table 1. Components of CHAMPS Pilot delivered over the 3-month intervention period**

10 sessions with the CHW	Detailed in Table 3 below
CleverCap	Participants and CHW will be able to track ART adherence.
WiseApp	
 
CHW will be able to deliver sessions to the study participants through the WiseApp.
 
Participants will be able to self-manage their health through the content described in Table 2.
 
Participants and CHW can securely chat with one another.
 

**Intervention Training and Support.** The CHW will be trained on the intervention: content of each session, MI, strengths-based case management, ARTAS, HIV and substance

use, and safety in the field. The CHW will also be trained on use of the WiseApp and CleverCap assuring all study participants and CHW are able to successfully use the mHealth technology. Training for the CHW will also be provided on: human subjects research protection, financial conflict of interest, HIPAA, and data privacy and security. The CHW will engage in supportive strengths-based case management and MI with the study participant. Intervention visits (~ten over a 3-month period) will help participants access primary medical care by acknowledging and addressing barriers to care. Participants will participate in CHW sessions via the App. This will help participants overcome many of the challenges to participating in-person, which has been a frequent barrier due to COVID-19.

The WiseApp offers the following functionality listed in Table 2, and the CleverCap is linked to the WiseApp. The CleverCap fits on standard pill bottles, dispenses only the prescribed amount of medication, keeps track of medications dispensed, and communicates wirelessly with mobile devices. Participants are then able to self-monitor their medications, and the CHW will also be able to track study participants' adherence to their ART medication in real time. Participants receive reminders through the WiseApp when they have not taken their medication on time and receive encouraging messages (e.g., Great job! You've met your goal for not forgetting your meds) when they have taken their medication.

Communication via the App will enhance the relationship between the CHW and the study participant.

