**Table 3. Outline of CHW Sessions with study participants guided by BA2C and ARTAS content**

Title		Sample Content for Each Session
1	Building the Relationship	Introduce the goals of CHAMPS Pilot
2	Introduction to the WiseApp	Discuss how the App can be used to facilitate communication between the CHW and the provider. Review the medication tracking function and how this can be used by the CHW and the participant.
3	Emphasizing Personal Strengths	To help the patient self-identify personal strengths, abilities, and skills.
4	Learning to Make Contact	Assist patient in preparing a list of questions to ask care provider
5	Reminder Call	Call at the agreed upon time; Remind participant of any needed documents
6	Primary Care Provider Appointment #1	Support patient's efforts remotely during care provider visit
7	Debriefing Provider Visit with Client #1	Solicit patient's input on what went well for the patient. Elicit from the patient what he or she learned from the care visit and what strengths he or she demonstrated during the care visit.
8	Reviewing Progress	Plan for and review the transition process between the CHW and study participant
9	Debriefing Provider Visit with Client #2	Solicit patient's input on what went well for the patient. Elicit from the patient what he or she learned from the care visit and what strengths he or she demonstrated during the care visit.
10	Completing the work	Review the transition process/ Transition to long term/Ryan White case manager or other providers

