### Study Outcomes

The study outcomes are described in Table 4. The primary outcome of the study is viral suppression which will be operationalized as viral load  $\leq 50$  at 3 months. Viral load is the biologic correlate of the ART adherence behavior; yet, to achieve biologic change, there must be change in the adherence behavior. As suggested through the "Undetectable equals Untransmittable," or "U=U," public health campaign, PLWH who take ART as prescribed and achieve and maintain viral suppression have effectively no risk of sexually transmitting the virus to a serodiscordant partner. Our secondary and related outcomes include ART adherence measured in two ways: 1) a single-item self-report measure, an empirically validated instrument, and 2) electronic pill bottle data, collected via the CleverCap bottle. The electronic

pill bottle data provide a less subjective measure as compared to self-report. We will also measure missed healthcare visits using electronic medical record (EMR) data.

Limitations and Considerations of the Study Outcome. We recognize that all the approaches for measuring viral suppression and ART adherence are limited. First, viral suppression does not directly measure a behavioral outcome but, rather, the biologic effects of the behavior. Second, the self-report measure is biased

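### Does a follow-up window opening 30 days before the 3-month target undermine the primary viral load and the exit interviews?

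*Combined protocol and SAP*

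**What the plan says.** The programme is described under Design Overview: "The CHAMPS Pilot intervention, outlined in Table 1, is a 3-month intervention guided by BA2C". The text following Table 1 gives its intensity: "Intervention visits (~ten over a 3-month period) will help participants access primary medical care". No calendar for the sessions is given. Under Procedures the first CHW meeting takes place "generally on the same day but no more than five business days" after assignment. Table 3 ends with progress review (session 8), a second debrief after a provider visit (session 9) and a closing session: "Review the transition process/ Transition to long term/Ryan White case manager or other providers".

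There is one post-baseline assessment, at 3 months, in both arms (Procedures; Table 4). It supplies the primary endpoint: "The primary outcome of the study is viral suppression which will be operationalized as viral load" of at most 50 at 3 months (Study Outcomes). The Aim 2 interview is attached to it: "Participants will also be provided the opportunity to complete a follow-up interview at their follow-up visit".

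Overview of Data Collection Time Points sets the window: "Follow-up visits will be scheduled 30 days before to 30 days after the target window based on participant availability and site capacity". The reason follows: "Timing of follow-up visits is scheduled to allow site flexibility while still scheduling follow-up visits within a reasonable time span". No section requires the sessions to be complete before the visit, and none sets a separate window for the blood spot or the interview.

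**The concern.** Taking 3 months as about 90 days, the earliest permitted visit is near day 60, when roughly a third of the intervention period is still to come. Only the intervention arm can lose planned exposure in this way; the control arm has no programme to cut short. A late visit does not shorten exposure, so the early half of the window looks like an avoidable cost.

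Two things would be at stake. Sample Size and Power Calculation says the pilot is to inform the effect size for later efficacy trials, and an effect measured on a partly delivered programme would be too small. And a participant interviewed before sessions 8 to 10 cannot comment on them, although the interviews are meant to guide changes to the programme.

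**Working it through.** The plan states no figure that can be reproduced here: it gives no suppression rates, effect size or power. The check is therefore calendar arithmetic followed by a sensitivity calculation.

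**Inputs from the plan.** Window of 30 days either side; 3-month intervention; about ten sessions; first meeting within five business days (about 7 calendar days); 40 participants, 1:1; 20% attrition.

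**Assumptions.** Target at day 90 from randomisation; visit days uniform over the window; suppression of 30% in the control arm against 40%, 50% or 60%.

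**1. Exposure at the earliest visit.** 60/90 = 0.67 of the period, or (60 − 7)/90 = 0.59 if the 3 months start at a first meeting on day 7. With sessions 10 days apart, 7 of 10 are done by day 60 (first on day 0) or 6 of 10 (first on day 7). With weekly sessions, 9 or 8 are done by day 60 and the last falls on day 63 or 70. A visit can therefore precede the last session under each pacing, but the number missed ranges from 1 to 4.

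**2. Mean effect relative to day 90**, with linear growth up to day 90:

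| After day 90 the effect | Existing window, days 60–120 | Window opened at day 90, days 90–120 |
|---|---|---|
| levels off | ½ × (75/90) + ½ × 1 = 0.917 | 1.000 |
| keeps growing | 90/90 = 1.000 | 105/90 = 1.167 |
| declines at the same rate | ½ × 0.833 + ½ × 0.833 = 0.833 | 1 − 15/90 = 0.833 |

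The later window is better in the first row, worse in the second and no different in the third. Nothing in the plan says which row applies.

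**3. Size of the loss in the least favourable row for early visits (levelling off).** With a share p of visits before day 90, the mean effect is 1 − p × (1 − 0.833): 0.983, 0.958 and 0.917 for p = 10%, 25% and 50%. At p = 50% the loss is (1 − 0.917) × 10, 20 or 30 points = 0.8, 1.7 or 2.5 points. A harsher case puts half of all visits exactly at day 60: 30 × (0.5 + 0.5 × 2/3) = 25, a loss of 5 points.

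**4. Precision.** Completers per arm: 40 × 0.8 / 2 = 16. Half-width = 1.96 × √[(p₁(1 − p₁) + p₂(1 − p₂))/16]. For 30% against 50% this is 1.96 × √(0.46/16) = 0.332; for 30% against 40% or 60% it is 1.96 × √(0.45/16) = 0.329. Each is about 33 points.

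**5. Sensitivity to pacing.** With weekly sessions, effect proportional to sessions delivered and level afterwards, a first session on day 0 leaves one session outstanding for 3 of the 60 days: 1 − 0.1 × 3/60 = 0.995. A first session on day 7 leaves two outstanding for 3 days and one for 7 days: 1 − 0.2 × 3/60 − 0.1 × 7/60 = 0.978. Even for a 30-point difference the loss is then at most about 0.022 × 30 = 0.7 points. This counts sessions only; app and pill-bottle use would continue.

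**6. Cost of removing the early half.** The window falls from 61 to 31 calendar days. If that cost one completer per arm, the half-width for 30% against 50% becomes 1.96 × √(0.46/15) = 0.343, which is 1.1 points wider. That is of the same order as the 0.8 to 2.5 points to be gained.

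**The case for a change.** The strongest opposing case rests on the interviews, because it needs no model of how the effect grows. Someone seen near day 60 cannot describe sessions not yet held; there are at most 25 interviews, with intervention participants oversampled; and their content is meant to shape the programme. One can add that all visits are remote, so early slots seem easy to give up, and that late slots supply flexibility without cutting exposure.

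The facts in this stand; the inference is weak. The interviews are optional and Aim 2 directs them largely at recruitment, enrolment and retention, with acceptability alongside. Of the three closing sessions, session 9 has the same sample content as session 7. Late visits have their own cost: they measure after support has ended, and if the effect fades they dilute it as much as early ones do. Flexibility is not free to surrender either. The team's earlier CHW trial retained 70%, and this plan counts on 80%. Human Subjects Involvement, Characteristics, and Design also gives a total study duration of 3 months. The existing late half already passes that limit, and a window opening at day 90 would make later visits the norm.

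Reporting the actual collection day by arm and the sessions delivered by then would be informative and would use data already collected. It is extra description and changes no conclusion.

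**Conclusion.** The concern does not hold. The early half of the window does allow the endpoint and the interview to precede the last sessions, but the consequence is small and the alternative is not shown to be better. Under the one trajectory where early visits do harm and a later window helps, the loss is 0.8 to 2.5 points for true differences of 10 to 30 points. It is 5 points if half of all visits fall on the earliest day with a 30-point difference. The half-width is about 33 points. Under weekly pacing the loss nearly disappears. The randomised comparison remains valid as long as visit timing is similar in the two arms, and the plan applies the same window to both.

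The result depends on reading the undefined target as day 90, on uniform visit days and on assumed suppression rates. A session calendar or a marked difference in visit timing between arms could change the size. As planned, the window is a deliberate choice with a stated reason, and reasonable statisticians could differ on it.
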